8.0 SELECTION CRITERIA FOR DATA COLLECTION

8.1 DATA SELECTION CRITERIA for phase 1

There will be no exceptions (waivers) to eligibility criteria for data inclusion into the study.

The criteria have been carefully considered and are standards used to ensure the data can be appropriately selected, collected and appropriately analysed. It is therefore vital exceptions are not made to the following detailed selection criteria.

8.1.1 INCLUSION CRITERIA

Patients to be included in this phase 1 of this study must fulfil all of the following criteria:

- Adult patients >18 years old (indicated from patient details) admitted to RFH ITU from the 1st of April 2020 until the 30th of October 2020;
- Intubated and ventilated (indicated from documentation in notes);
- Ventilated with anaesthetic machine during their admission (as suggested by daily nursing observation charts and daily review sheets in the notes of ICU clinicians and physiotherapists).

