3.0 STUDY SUMMARY

Official title:	Evaluation of the impact of using anaesthetic machines for ventilation on COVID-19 patients and professionals. A mixed methods study.
Brief title /Acronym:	COVID19 AnMach
Sponsor reference number:	133491
Study Population/disease condition	Phase 1. Patients ventilated on anaesthetic machines during COVID-19 surge in April and May 2020. Phase 2. Professionals who managed patients on an anaesthetic machines on the above-mentioned period.
Research Question	What is the impact of ventilating patients on an anaesthetic machine?
Study design	Observational non-interventional retrospective data collection, survey and qualitative study
Eligibility criteria:	
Inclusion criteria:
 
Phase 1. Adult patients >18 years old admitted to RFH ITU from the 1st of April 2020 until the 30th of October 2020; ventilated with an anaesthetic machine during their ITU admission.
 
Phase 2. ITU professionals who managed patients ventilated using anaesthetic machines at the RFH ITU between the same period.
 
Exclusion criteria:
 
Phase 1. Patients ventilated with ITU grade ventilators from admission.
 
Phase 2. Professionals who did not managed patients on an anaesthetic machine.

Anticipated start date	01/07/2020
Anticipated end date	30/11/2020
Target number of subject's/data sets	Maximum 15 patients related datasets
Target number of participants	Maximum 20 professionals' interviews
Primary aim	The study aims to identify issues with ventilation of COVID-19 positive critically ill patients on anaesthetic machines that are not described in available guidelines.

	Adverse events affecting patient's management and the staff experience of using anaesthetic machines are explored.
Sources of funding	Royal Free Charity
Sponsor	Royal Free London NHS Foundation Trust
Contact name	Sponsor representative : [name] Email: [contact] [contact] Fax : NA Chief Investigator: [name] Email: [contact] [contact] Fax: N/A

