5.2 RATIONALE

In order to meet the increased demand for ITU beds, in many hospitals in the UK, and in particular at the RFH, general care wards were transformed into ITUs in preparation for the surge. The ward 2North A (2NA) and the main recovery room at the RFH has been equipped with AnMach with a view to admit COVID-19 surge ventilated patients. Patients were looked after by either anaesthetic or intensive care consultants as well as ITU and non-ITU nurses and doctors.

Evidence around the use of AnMach for long-term ventilation and weaning of critically ill patients is scarce. Published studies are dated and based on test lung model and compare the performance of the AnMach and ICU ventilators in the laboratory settings (Jaber et al., 2006; Tung et al., 2005). Despite recently disseminated guidelines, professionals who managed surge patients admitted to 2NA/main recovery may have not been familiar with the equipment and not been aware of the newly published evidence.

This study aims to explore the clinical outcome of patients admitted to 2NA/main recovery in April and May 2020, identify possible adverse events related to the use of AnMach as ventilators, and capture the experience of staff using unfamiliar equipment and managing non typical cases. The results of our study will potentially allow us to identify additional risks of using AnMach as ITU ventilators rather than the ones published in the guidelines and to recognise hidden areas for improvement of care and staff support to address.

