7.1 METHODS

This project consists of two parallel phases:

Phase 1, a quantitative, observational, cohort study to detect the effect of exposure to anaesthetic machine ventilation of COVID-19 patients in term of adverse events.

The quantitative phase may be also divided in two parts:

1a, a retrospective data collection of patients admitted to RFH ITU (and possibly the Barnet Hospital ITU) and connected to anaesthetic machines between the 1st April and 1st June 2020, and

1b, a prospective data collection of cases that occur between the 1st June and the 30th October 2020 in order to cover a new period of possible COVID-19 surge.

Phase 2, a survey and an interview stage engaging ITU professionals that managed patients on anaesthetic machines during the COVID-19 surge in an unfamiliar environment (nurses, physiotherapists, and doctors).

Mixed methods were chosen to integrate elements of quantitative and qualitative research in order to achieve a broader understanding of the topic. Also using both methods and integrating results helps determining the interview phase sample and interpreting the findings of the quantitative phase (O'Cathain et al., 2007).

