This involves applying the inclusion criteria listed above to patients admitted to 2NA and main recovery between the 1st April 2020 and 1st June 2020. The list of these patients will be generated using the records from the Cerner EPR Computer System where all patient locations within the hospital are updated in a 'live' fashion. This will give us an accurate picture of all the patients admitted to 2NA and main recovery during the above period thus providing a population of patients who were exposed to ventilation by AnMach. In order to identify individuals who were ventilated by AnMach while in this location, we will review the nursing charts and the physiotherapy notes which we anticipate will provide evidence for the method ventilating a particular patient in that location of the hospital

2. Review of raw data:

Following identification of study participants using the inclusion criteria (Section 8.1.1), data from their admission will be reviewed and collected. This will involve manual review of the following:

- Observation charts (when released for review). These provide quantitative data and trends can be identified to provide evidence that ventilatory support was being weaned or escalated:
 - These charts will show hour by hour trends in the level of respiratory support being delivered to the patients, including; the mode of ventilation, the delivered oxygen concentration, the pressure settings of ventilation, position of the patient (i.e. whether prone or not).
 - They also show the physiological status of the patient including their hourly observations and regular blood gas sampling, thus providing evidence about

- whether the patient was deteriorating, improving or remaining static in terms of ventilatory support.
- The chart may also provide qualitative evidence of a patient weaning from ventilation. The back of the chart provides space for the nursing staff to record information regarding the course of the day using 'free-hand'. This will provide evidence of the ventilator being used as well as the clinical direction of the patient i.e. whether weaning or not.
 - Daily review sheets filled in by ICU clinicians and physiotherapists.

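### Phase 1 dates entry to one cohort by three different events, so a patient admitted to ITU before 1 April 2020 and first put on an anaesthetic machine in April or May is in under some sections and out under others

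*Protocol*

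**What the plan says.** The phase 1 inclusion criteria (protocol section 8.1.1) open by saying that patients "must fulfil all of the following criteria". The first criterion carries the only date: "admitted to RFH ITU from the 1st of April 2020 until the 30th of October 2020". The exposure criterion, "Ventilated with anaesthetic machine during their admission", has no date of its own. Section 8.1 adds: "There will be no exceptions (waivers) to eligibility criteria for data inclusion into the study".

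Other sections describe the same cohort by other events:

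- The population row of section 3.0 uses exposure: "Patients ventilated on anaesthetic machines during COVID-19 surge in April and May 2020". The eligibility row of the same table goes back to the ITU admission date.
- Section 7.1, part 1a, joins ITU admission with being "connected to anaesthetic machines between the 1st April and 1st June 2020".
- Section 5.2 uses location; the study is to "explore the clinical outcome of patients admitted to 2NA/main recovery in April and May 2020". Section 6.2 also uses location, but runs to 30 October.
- Section 9.1.1a, Option II, which the protocol treats as the operative case, takes adverse events from the charts of everyone admitted to 2NA/main recovery from 1 April to 1 June. The identification step that follows then means "applying the inclusion criteria listed above to patients admitted to 2NA and main recovery between the 1st April 2020 and 1st June 2020".

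Section 8.1.2 separately excludes anyone on an ITU-grade ventilator from admission. Section 13.1.2 lists, as a secondary endpoint, the count of patients ventilated with an AnMach over the period studied.

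**The concern.** ITU admission, start of AnMach ventilation and arrival in 2NA/main recovery can fall on different days for one patient. If ITU admission falls before 1 April and the other two fall after it, the sections disagree on whether the patient belongs to the study. Two people abstracting charts could each follow the protocol and build different cohorts, and the no-waiver rule leaves no room to settle the matter case by case.

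At stake are the denominator of both primary proportions and the section 13.1.2 count, which is a count of exposure but would be drawn from a cohort defined by admission. The two phases also differ: phase 2 admits staff because they managed AnMach patients from 1 April, so a nurse could be eligible through a patient who is not.

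**Working it through.** The protocol offers no calculated figure to reproduce: section 13.2 states that there is no sample size calculation. The check is a comparison of the sections, followed by simple bounds.

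**Step 1: one hypothetical patient against each rule.** Suppose a patient is admitted to RFH ITU on 30 March 2020 without a ventilator, moves to 2NA on 3 April, and is intubated there on an AnMach. The ITU-ventilator exclusion in section 8.1.2 does not apply.

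| Protocol section | Event that is dated | Window (2020) | Patient |
|---|---|---|---|
| 3.0, population row | AnMach ventilation | April and May | in |
| 3.0, eligibility row | ITU admission | 1 April to 30 October | out |
| 5.2 | admission to 2NA/main recovery | April and May | in |
| 6.2 | admission to 2NA/main recovery | 1 April to 30 October | in |
| 7.1, part 1a | ITU admission and AnMach connection share one window | 1 April to 1 June | in if the dates govern connection only; out if they govern both |
| 8.1.1 (phase 1) | ITU admission | 1 April to 30 October | out |
| 9.1.1a, Option II | admission to 2NA/main recovery, all patients | 1 April to 1 June | in |
| 9.1.1a, identification step | the location list, then the 8.1.1 criteria | 1 April to 1 June | out |
| 13.1.2, AnMach count | AnMach ventilation | study period | in |

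**Step 2: who is affected.** Only patients who meet all three conditions: admitted to ITU before 1 April, not on an ITU-grade ventilator from admission, and first ventilated on an AnMach in April or May. Patients on an ITU-grade ventilator from admission are removed by section 8.1.2 whatever the date.

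**Step 3: possible effect on a proportion.** Take N = 15 exposed patients. Section 3.0 gives 15 as the maximum number of datasets, so using it as the exposed total is an assumption. Let k be the number left out by the date rule, which the documents do not give, and x the number with the event among the N − k included.

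- Reported proportion: x/(N − k).
- Full-cohort proportion: between x/N and (x + k)/N, an interval of width k/N.
- Largest shift: k/N, reached when the reported proportion is 0% or 100%.

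Results:

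- k = 0: no effect.
- k = 1: 1/15 = 6.7 percentage points at most.
- k = 2: 2/15 = 13.3 points at most.
- k = 3: 3/15 = 20.0 points at most.

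These are ceilings. With k = 1 and x = 7, the reported value is 7/14 = 50.0% and the full-cohort value is 7/15 = 46.7% or 8/15 = 53.3%, a shift of 3.3 points. If the 15 are all included patients and one more is left out, the ceiling is 1/16 = 6.25 points.

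**The case against.** The case for leaving the text alone has several parts.

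- **The affected group is narrow and may be empty.** Section 8.1.2 already takes out those on an ITU-grade ventilator from admission. Section 5.2 says the surge area was set up for ventilated patients, which fits poorly with someone arriving there before intubation. This stands: no section shows that such a patient existed.
- **The wording can be read so that the conflict shrinks.** Section 5.2 says wards were turned into ITUs. If admission to ITU covers entry to 2NA/main recovery, the hypothetical patient qualifies. Section 7.1 can be read as requiring both events in the window, and the population row of section 3.0 may be only a short label. These readings are possible, but the protocol never states them. Section 9.1.1a records a date of ICU admission, and section 13.1.2 measures ICU stay from it, without saying that it means arrival in the surge area.
- **An admission-date window is an ordinary choice for a descriptive chart review with no planned comparison.** True. The difficulty is not that choice but the use of other events for the same cohort.

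A reader might go further and infer that the criterion strips out the earliest AnMach use, when staff were least practised and before the national guidance, and so biases the findings. The documents do not support that. They do not say that the first AnMach patients were already in ITU; new arrivals could equally have been the overflow. Section 5.1 dates the NHS England guidance to the end of April, so admissions from 1 April onward already cover nearly all of April before it appeared.

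**Conclusion.** The inconsistency is real and lies in the text: three entry events and two end points (the end of May or 1 June, against 30 October) are used for one phase 1 cohort. Under the literal criteria and the no-waiver rule, a narrow group is excluded although other sections include it.

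The size is unknown and may be nil. If such patients exist, each could move a proportion by at most about 6.7 percentage points, assuming 15 exposed patients in all, and would lower the section 13.1.2 count by one. It would be wrong to conclude that everyone in ITU on 1 April who later went onto an AnMach is lost through the date rule, or that a particular share of the cohort is missing. The first overlooks section 8.1.2; the second needs a number that the documents do not contain. The point calls for reconciling the sections and is not evidence of a biased result.

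**What to change.** In sections 3.0 (eligibility row) and 8.1.1, replace the ITU-admission-date condition with presence in 2NA/main recovery on the Cerner location record, and AnMach ventilation during that stay, within the study window and whatever the date of ITU admission. Use 1 April to 1 June 2020 for part 1a and keep 1 June to 30 October 2020 for part 1b, assigning 1 June itself to one part only. Align sections 5.2, 6.2, 7.1 and 9.1.1a with this wording.

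Dating entry by location is preferable to dating it by AnMach start. Section 9.1.1a warns that charts may not show which device was used, and the data list there has no AnMach start date, whereas the location record is already the planned source for finding patients. Keep ITU admission date as a recorded variable, and add AnMach start date where the charts show it.

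The cost is a protocol edit, one added field and possibly a few more charts to abstract.

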8.1.2 EXCLUSION CRITERIA

- Any patient who received treatment in intensive care and was ventilated with an ITU grade ventilator from admission

8.2 PARTICIPANT SELECTION CRITERIA for phase 2

There will be no exceptions (waivers) to eligibility criteria prior to participant inclusion into the study. Any questions raised about eligibility should be addressed prior to entering the participant.

The eligibility criteria have been carefully considered and are standards used to ensure the trial results can be appropriately used to make future treatment decisions for other people with similar disease or medical condition. It is therefore vital exceptions are not made to the following detailed selection criteria.

All participants that are screened for inclusion into the study must be entered onto the sponsor screening log RFLRDLOG0001 and will be assigned a sequential number. Participants will be considered eligible for enrolment into this trial if they fulfil all of the inclusion criteria and none of the exclusion criteria as defined below.

Eligible participants will be entered onto the sponsors Subject ID log RFLRDLOG0002 and assigned a Trial specific Identification number in a pre-agreed format in accordance with Site identifier and next sequential numerical value e.g. RF001

8.1.1 INCLUSION CRITERIA

- ITU professionals (nurses, physiotherapists, ITU consultants trained in intensive care and who that are not accredited anaesthetists) who agree to be interviewed and manifest their consent responding to the survey;
- ITU professionals who managed patients ventilated using anaesthetic machines at the RFH ITU between the 1st April and the 30th of October 2020;

8.1.2 EXCLUSION CRITERIA

- ITU professionals who didn't manage patients on anaesthetic machines

8.1.3 DISCONTINUATION/WITHDRAWAL OF PARTICIPANTS

Any study participant is free to withdraw from the study at any time. Collected material pertaining to the participant will be destroyed and their details erased from the database.

9 STUDY PROCEDURES

9.1 PHASE 1 PROCEDURES: quantitative cohort study

9.1.1a - Retrospective data collection

The quantitative phase of this study aims to broadly examine the impact of using anaesthetic machines for ventilation of COVID-19 positive patients.

Important note: current inability to access the patient notes and observation charts (access to notes is requiring a quarantine period once a patient has been discharged from ITU; this is currently 2 weeks) may lead to partial availability of the data described in the endpoints section. Anecdotal evidence from discussions with nursing staff suggests that it may not be possible to tell from the documentation which patients were ventilated with AnMach versus a conventional ITU ventilator. This issue can only be addressed following accessing some of the observation charts that have been processed and released from quarantine. At this moment we can hypothesise two options:

Option I, we can label the charts as AnMach use: It will be possible to perform a clinical outcomes and adverse events comparison between patients identified as being ventilated by AnMach and those

identified as being ventilated by conventional ICU ventilators. In this case (less likely) we will request a study amendment after having access to the chart and being sure we can achieve this. We will also request an amendment in case of a second surge of COVID19 for the prospective data collection.

Option II, we cannot distinguish which device was used to ventilate the patients: adverse events possibly linked to AnMach will be recorded from charts of all patients admitted to 2NA and main recovery between the 1st April and the 1st of June 2020. We will also review Datix database for any serious incidents related to the use of AnMach.

The remaining sections refer to this option II = we cannot label charts as AnMach (more likely to be the case).

The Methods for Phase 1 of this study can be broken down into the following sections:

1. Identification of study participants:

This involves applying the inclusion criteria listed above to patients admitted to 2NA and main recovery between the 1st April 2020 and 1st June 2020. The list of these patients will be generated using the records from the Cerner EPR Computer System where all patient locations within the hospital are updated in a 'live' fashion. This will give us an accurate picture of all the patients admitted to 2NA and main recovery during the above period thus providing a population of patients who were exposed to ventilation by AnMach. In order to identify individuals who were ventilated by AnMach while in this location, we will review the nursing charts and the physiotherapy notes which we anticipate will provide evidence for the method ventilating a particular patient in that location of the hospital

2. Review of raw data:

Following identification of study participants using the inclusion criteria (Section 8.1.1), data from their admission will be reviewed and collected. This will involve manual review of the following:

- Observation charts (when released for review). These provide quantitative data and trends can be identified to provide evidence that ventilatory support was being weaned or escalated:
 - These charts will show hour by hour trends in the level of respiratory support being delivered to the patients, including; the mode of ventilation, the delivered oxygen concentration, the pressure settings of ventilation, position of the patient (i.e. whether prone or not).
 - They also show the physiological status of the patient including their hourly observations and regular blood gas sampling, thus providing evidence about

- whether the patient was deteriorating, improving or remaining static in terms of ventilatory support.
- The chart may also provide qualitative evidence of a patient weaning from ventilation. The back of the chart provides space for the nursing staff to record information regarding the course of the day using 'free-hand'. This will provide evidence of the ventilator being used as well as the clinical direction of the patient i.e. whether weaning or not.
 - Daily review sheets filled in by ICU clinicians and physiotherapists.
 - These will provide more information about the progress of patients while being ventilated. There may be documentation that mentions difficulties that have arisen when ventilating or weaning ventilation in these patients as well as providing indications as to why patients have been switched to different modes of ventilation or device.
 - Physiotherapists' notes may help us to identify the AnMach patients.

3. Data recording and translation to Outcomes/Endpoints

The data for each patient will be recorded and anonymised in an encrypted Excel spread sheet and will include:

- Age, gender
- Reason for admission
- APACHE II score
- SOFA score
- Date of admission to ICU
- Date of intubation
- Was patient ventilated using AnMach?
- Number of days of ventilatory support before weaning ventilation
- Number of days spent weaning from ventilation to being successfully weaned from ventilator (extubation)
- Was patient transferred from AnMach onto conventional ICU ventilator?
- How many days following ventilation with the AnMach did the transfer happen?
- What was the indication for transferring a patient from an AnMach to the conventional ICU ventilator?
- Did the patient receive a tracheostomy?
- Adverse events possibly correlated with the use of AnMach: soda lime issues, gas flow issues, hypoxia, elevate pressure of ventilation, water need to be cleaned out of tubes, sudden respiratory rate increase, need for manual ventilation
- Organ support - number of days of
 - Use of one or more inotropic drugs or anti arrhythmic

- Renal - a need for renal replacement therapy
- Liver - correction of coagulopathy (plasma use), hypoglycaemia (glucose use), presence of hyperlactataemia (high lactate levels) related to liver failure
- Neuro - delirium
- Date of discharge from ICU or date of death
- Length of ITU stay

The above data will be used to identify quantitative values for the primary and secondary endpoints discussed in section 13.1. This will then be analysed as discussed in Section 13.0

9.1.1b - a prospective data collection

Prospective data may be suitable for collection depending on the course of the COVID-19 crisis. At present there are no patients at the Royal Free Hospital being ventilated on anaesthetic machines. However, if there is a 'second surge' in cases and the department is forced to re-expand and use anaesthetic machines for ventilation then there may be scope to develop a prospective element to data collection. Should there be patients being ventilated with anaesthetic machines in the future, we would consider a prospective cohort study to examine outcomes for patients ventilated by anaesthetic machines and request an amendment of the study protocol to HRA.

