13.1 Phase 1 ENDPOINTS

13.1.1 PRIMARY ENDPOINTS

- Proportion of patients who experienced any of the following adverse events possibly correlated with the use of AnMach: soda lime issues, gas flow issues, hypoxia, elevate pressure of ventilation, water need to be cleaned out of tubes, sudden respiratory rate increase, need for manual ventilation (frequency).
- Proportion of ventilation weaning failure while on AnMach (frequency) – This is defined as meeting one of the following criteria:
 - Lack of progress on AnMach – Defined as a failure to reduce ventilatory support for period of > 48 hours
 - Need for ventilation on an ITU grade ventilator – This will be a measured event of the transfer from AnMach to ITU-grade ventilator

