13.2 STATISTICAL ANALYSIS PLANS

The retrospective (and prospective, if available) data collection:

This is a cohort study with no sample size calculation. The number of patients managed on AnMach and charts available (identified as AnMach Use) will dictate how many cases we will be able to analyse. The statistical analysis will be descriptive and performed with the Microsoft Office Excel data analysis package in case we will not be able to identify the AnMach charts and we will collect only adverse events data and report them as proportions. The clinical outcomes will be described using absolute and relative frequencies (expressed as a percentage) or position indices (average or median) and relative dispersion indices (standard deviation or interquartile range) suitable for the type of variable analysed. If comparison between AnMach patients and ITU ventilator patients will be possible, mean and standard

23

deviation of clinical outcomes for the two groups will be compared (the plan for this analysis will be explained in case of requesting a protocol amendment).

The Survey:

The questionnaire answers will be inserted in an excel spreadsheet and cleaned. Incomplete, inaccurate and missing data will be detected and discussed during interviews. The results will be used to select participants for the second stage and implement the topic guide for interviewing the volunteers. For this aspect of the study the statistical analysis will be descriptive and performed with the Microsoft Office Excel data analysis package. Data will be reported as proportions.

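### Under Option II the protocol gives two different denominators for the first primary endpoint, sets no on-device time window for its events, and keeps a second primary endpoint that needs the missing device label

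*Protocol*

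**What the plan says.** Protocol Section 9.1.1a sets out two cases. In Option I the charts can be labelled by device, and an amendment would follow. The other case is "Option II, we cannot distinguish which device was used to ventilate the patients". There, "adverse events possibly linked to AnMach will be recorded from charts of all patients admitted to 2NA and main recovery between the 1st April" and 1 June 2020, with a search of the incident database alongside. The section then says which case governs: "The remaining sections refer to this option II = we cannot label charts as AnMach (more likely to be the case".

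Phase 1 eligibility (Sections 8.1 to 8.1.2) is strict: "There will be no exceptions (waivers) to eligibility criteria for data inclusion into the study". One criterion is "Ventilated with anaesthetic machine during their admission", as evidenced by nursing charts and review sheets. Patients on an ITU-grade ventilator from admission are excluded.

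The rest of 9.1.1a, which by its own statement falls under Option II, applies the inclusion criteria to the list of patients in the two locations. It looks to nursing charts and physiotherapy notes to find who was on AnMach. For the patients so identified, "data from their admission will be reviewed and collected". The data list has a field for AnMach use and fields for the fact, timing and reason of a transfer to a conventional ventilator.

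Section 13.1.1 has two primary endpoints. One is the proportion of patients with any of seven listed adverse events. The other is "Proportion of ventilation weaning failure while on AnMach (frequency", met by no reduction in support for more than 48 hours or by transfer to an ITU-grade ventilator. Section 13.2 plans a descriptive analysis "in case we will not be able to identify the AnMach charts and we will collect only adverse events data and report them as proportions".

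**The concern.** The protocol itself fixes the population, the endpoints and the fallback rule, and the three do not fit together in the scenario that it calls more likely. This is not a detail that can be left to an analysis plan.

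- **Who is counted.** Two people following the text could build two different denominators for the first primary endpoint.
- **When events are counted.** Nothing limits events to time on the device. Several of the seven events can happen on any ventilator.
- **Whether the second primary endpoint exists.** It needs device identity by patient and by time, which Option II assumes is unavailable.

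At stake is what the reported proportion means. A figure built from location alone could be taken as an event rate on anaesthetic machines, and one of the two primary endpoints could drop out without Section 13.1 saying so.

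**Working it through.** The protocol states that there is no sample size calculation, and it gives no event rate, so there is no figure to reproduce. The check sets the sections side by side and then uses assumed inputs to show scale.

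**Step 1: denominator.**
- 9.1.1a, Option II statement: device unknown, all admissions to the two locations.
- 8.1 to 8.1.2: AnMach ventilation required, ITU-grade ventilator from admission excluded, no waivers. Both rules need the device to be known.
- 9.1.1a, identification step: inclusion criteria applied and AnMach patients sought in the notes. The same step also calls the location list an exposed population.

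The first and third give different patient sets. If Option II's premise is fully true, the third cannot be carried out. If it is only partly true, no rule says what to do with patients whose device stays unknown.

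**Step 2: event window.** Endpoint 1 carries no on-device restriction, whereas endpoint 2 does. Data come from the admission, and the data list expects transfers to ITU ventilators. Soda lime problems are specific to AnMach. Hypoxia, raised pressure, a sudden rise in respiratory rate and manual ventilation are not.

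**Step 3: endpoint 2.** The transfer criterion needs the device before and after. The 48-hour criterion can be read from any chart, but placing it on AnMach needs the device. Section 13.2 says only adverse events would be collected without labels, while Section 13.1.1 attaches no condition.

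**Step 4: scale. All rates, counts of events and durations here are assumptions; only the maximum of 15 datasets comes from the protocol (Section 3.0).**

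*Mixing patients.* Reported proportion = q × pA + (1 − q) × pI, where q is the share truly on AnMach, pA the event risk on AnMach and pI the risk of look-alike events otherwise. Take pA = 60%.

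| q | pI = 0% | pI = 20% | pI = 60% |
|---|---|---|---|
| 100% | 60% | 60% | 60% |
| 75% | 45% | 50% | 60% |
| 50% | 30% | 40% | 60% |
| 25% | 15% | 30% | 60% |

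For example, 0.5 × 0.60 + 0.5 × 0.20 = 0.40.

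*Counting the whole stay.* P(any event) = 1 − exp(−h × days), with a constant daily rate h of non-specific events, 5 days on AnMach and 15 ventilated days in all.
- h = 0.05: 1 − exp(−0.25) = 22% on device; 1 − exp(−0.75) = 53% over the stay.
- h = 0.10: 1 − exp(−0.5) = 39% on device; 1 − exp(−1.5) = 78% over the stay.

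In these examples mixing lowers the figure or leaves it unchanged, and the longer window raises it. The net sign is unknown.

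*Endpoint 2 without labels.* Suppose 6 of 15 patients meet the 48-hour criterion on some device, and k of the 15 were on AnMach. The AnMach-only proportion lies between max(0, 6 − (15 − k))/k and min(6, k)/k.
- k = 5: 0% to 100%
- k = 10: 10% to 60%
- k = 12: 25% to 50%
- k = 15: 40% exactly

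These bounds cover only not knowing which patients were on AnMach. Not knowing when they were on it adds to this.

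*Precision.* At the maximum of 15 datasets, 9/15 has an exact (Clopper-Pearson) 95% interval of 32% to 84%.

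**The case against.** The strongest reply is that the protocol does not simply analyse everyone admitted. The identification step, also under Option II, applies the inclusion criteria and looks for AnMach patients in the notes. Section 9.1.1a expects free-text entries on the charts to show the ventilator in use and physiotherapy notes to help. It warns that endpoint data may be only partly available, and that the device question can be settled only once charts are released. A device field already exists. Section 13.2 openly states the adverse-events-only fallback. Section 5.2 says the two areas were equipped with AnMach, so few patients there may have been unexposed. With at most 15 datasets and a purely descriptive aim, sampling error exceeds most of the shifts shown.

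Much of this stands, and it rules out several stronger readings. A reader might infer that ineligible patients will certainly be analysed in breach of the no-waiver rule; the text supports only a contradiction between two rules. A reader might infer that no device-dependent field can be filled; the protocol expects that some can. A reader might take whole-admission counting as a stated rule; it is inferred from the source of the data and the missing window.

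The reply does not remove the contradiction. The identification step relies on what Option II says cannot be done, and nothing covers patients left unlabelled. The device field has no rule for an unknown answer. The fallback in Section 13.2 is not carried into Section 13.1. Wide sampling error does not excuse an undefined denominator.

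**Conclusion.** The point holds as an internal contradiction that affects both primary endpoints in the scenario the protocol calls more likely. The denominator of endpoint 1 is either all location admissions or confirmed AnMach patients. Its event window is undefined, and endpoint 2 and the transfer endpoints are unconditional although they depend on a label that may be missing. These conclusions rest on the text alone.

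The size of any distortion does not. The illustrative figures depend on assumed risks, exposure shares and durations. If every patient in the two areas was on AnMach throughout ventilation, there would be no distortion. A reader might infer that the reported rate is too low because unexposed patients dilute it, or too high because off-device time is counted. The documents support neither direction.

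**What to change.** In Sections 9.1.1a and 13.1:

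- Replace the all-or-nothing options with a device status for each patient. Extend the existing AnMach field to three values: confirmed AnMach, unknown (location only), confirmed not AnMach. Exclude the last group.
- Report endpoint 1 for confirmed AnMach patients. Report location-only patients separately, labelled as a location-based proportion and not as an AnMach event rate. Add a sentence to Section 8.1 placing this group outside the eligible cohort, so that reporting it is not itself a waiver.
- Count events only during time on AnMach or, where the device is unrecorded, during time in 2NA or main recovery according to the electronic record's location entries.
- State that weaning failure and the transfer endpoints are reported for confirmed AnMach patients only, and are not reported if there are none. Align Section 13.2 with this.

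The cost is protocol wording and a change to one field; hourly charts and electronic location records are already named as sources. The confirmed set may be small or empty. If it is empty, only the location-based proportion is reported. Location remains a proxy for the device in the unknown group, which is why the separate label matters.
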